4.3. Interim Analyses

After all N=6 subjects are discharged from the clinic following Part 1, safety data will be examined as an informal review (not a formal IA).

A formal, unblinded IA will be performed on the PD2 population (Part 2 only) after at least 16 subjects have completed dosing in Part 2 and have been discharged from the unit, while enrollment may continue, for a possible final sample size of N=20 (N_{CP}). N_{CP} may be adjusted based on actual enrollment just before the IA decision but will not be less than 20.

It is assumed that baseline average daily ammonia is 70 µmol/L, and the placebo group will show a 0 – 10% reduction from baseline, while the desired reduction for the treatment group is 20% versus placebo. Furthermore, the assumed SD of the difference in the means (desired reduction) is 9 µmol/L. Additional assumptions were examined, and the operating characteristics at the IA for these more pessimistic possibilities are shown in Section 6.4.

If the p-value at the IA is < 0.028 the trial could be stopped for efficacy. Otherwise, conditional power (CP) will be computed at the IA for N=16 subjects. This is the probability that the trial will yield a statistically significant reduction in AUC of average daily ammonia change from baseline greater for the treatment group at the end of the trial if the observed difference at the IA is the TRUE underlying difference and the trial is continued to completion with a total of N_{CP} subjects. If this probability is less than 30%, the Safety Monitoring Committee (SMC) could suggest that the trial be stopped for futility. Otherwise, if the CP is less than 90% the sample size will be boosted to target a conditional power of 90%, up to a maximum of 40 patients. If the CP is greater than 90% and the p-value at the IA is greater than 0.028, the trial will end with N_{CP} subjects.

Conditional power for an active dose versus placebo is derived as follows:

$$C_p(\hat{\Theta}) = 1 - \Phi \left\{ \frac{c_2 - B(t)/t}{\sqrt{1-t}} \right\}$$

Parameter	Description
$\Phi\{x\}$	cumulative distribution function for a $N(0, 1)$ random variable
c_2	Adjusted critical cut-off for the final analysis. Assuming that alpha of 0.028 is spent at the interim analysis for one-sided testing, that the total one-sided alpha

	level is 0.05, and that only one IA occurs at the planned information fraction of 0.80 (=16/20), the adjusted critical cut-off is $c_2 = -1.904$.

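### SAP 4.3 prints a final cut-off of −1.904 where its own inputs give −1.726, and the SAP leaves the overall alpha and the interim efficacy threshold each with two values

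*SAP*

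**What the plan says.** **Final cut-off.** SAP 4.3 lists three inputs for c2: 0.028 spent at a single interim look, a one-sided total of 0.05, and the share of information available at that look. For the last of these, and for the result, it gives "the planned information fraction of 0.80 (=16/20), the adjusted critical cut-off is $c_2 = -1.904". The final test combines the two stages with weights √0.80 and √0.20 and rejects when Z_CHW falls below c2.

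**Overall alpha.** SAP 4.3 uses one-sided 0.05. SAP 4.2.1 puts all tests of primary and secondary endpoints at one-sided 0.10. SAP 4.2.5 and 6.4 give 0.10 overall, and SAP 4.1 and Protocol 10.5 give about 10%. None of these four names a side for the overall level.

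**Interim efficacy threshold.** SAP 4.3: "If the p-value at the IA is < 0.028 the trial could be stopped for efficacy". SAP 6.4 also uses 0.028 and calls it one-sided. SAP 4.2.5 names Haybittle-Peto and a p-value of 0.01.

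**Conditional power (CP).** SAP 4.3 prints CP as 1 − Φ{(c2 − B(t)/t)/√(1−t)}. Below 30%, "the Safety Monitoring Committee (SMC) could suggest that the trial be stopped for futility". Below 90%, the sample size is raised, to at most 40. With CP above 90% and no efficacy stop, enrolment finishes at N_CP. That number "may be adjusted based on actual enrollment just before the IA decision but will not be less than 20".

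**The concern.** c2 does two jobs. It is the final significance rule for ammonia AUC, and it enters the CP that drives futility and the increase to 40 subjects. If it does not follow from its stated inputs, both are off. If alpha and the interim threshold also differ between sections, the SAP does not determine the decision at an unblinded look, and a choice made after that look would be data-dependent. SAP 5 (changes to planned analyses) explains none of these differences.

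**Working it through.** **1. Recompute c2.** Inputs from SAP 4.3: interim alpha a1 = 0.028 one-sided (z1 = 1.911), total alpha A = 0.05 one-sided, t = 16/20 = 0.80. The weights give corr(Z1, Z_CHW) = √0.80 = 0.894. Under the null, with benefit negative, solve

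P(Z1 < −z1) + P(Z1 ≥ −z1, Z_CHW < c2) = A.

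| Interim alpha | A = 0.05 one-sided | A = 0.10 one-sided |
|---|---|---|
| 0.028 | −1.726 | −1.293 |
| 0.01 | −1.652 | −1.282 |

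The printed −1.904 is not reproduced. Other alphas, information fractions, two-sided versions, a Bonferroni split, and Pocock and O'Brien-Fleming boundaries were tried, and none gives it as a final boundary. It does equal an interim boundary: O'Brien-Fleming-type spending at one-sided 0.05 and t = 0.80 spends 2{1 − Φ(1.960/√0.80)} = 0.0284, z = 1.904. A swap of the two looks is possible, but that is inference, since 4.2.5 names Haybittle-Peto.

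**2. Error attained with −1.904.** Putting −1.904 into the same expression gives 0.0398 with a 0.028 interim and 0.0302 with a 0.01 interim.

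**3. Alpha and threshold.** A two-sided 10% is 5% per side, so the unsided figures agree with 4.3 only if they are two-sided. SAP 4.2.1 says one-sided 0.10, which cannot be read that way. An interim p between 0.01 and 0.028, say 0.02, permits an efficacy stop under 4.3 and 6.4 but not under 4.2.5.

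**4. Conditional power.** Rejection is at Z_CHW < c2, so the matching form is CP = Φ{(c2 − B(t)/t)/√(1−t)}, with B(t)/t = Z1/√t. At interim p = 0.08, Z1 = −1.405, Z1/√0.80 = −1.571 and √0.20 = 0.447.

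| c2 | (c2 + 1.571)/0.447 | CP at p = 0.08 | CP < 30% when p exceeds |
|---|---|---|---|
| −1.904 | −0.745 | 23% | 0.068 |
| −1.726 | −0.347 | 36% | 0.091 |
| −1.293 | 0.621 | 73% | 0.172 |

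**5. The 6.4 futility rates.** For each SD, I chose the drift that reproduces the printed efficacy-stop rate. In the normal model the drift is Φ⁻¹(rate) + 1.911, which is 1.569, 1.472, 2.045 and 4.285 at SD 26, 29, 20 and 9. Futility applies when |Z1| in the benefit direction is below √0.80 × (|c2| − 0.524 × 0.447). For c2 = −1.293 that bound is 0.947, so at SD 26 the rate is Φ(0.947 − 1.569) = 26.7%. The t(14) model (16 − 2 df) uses a noncentral t statistic, with the efficacy p-value also taken from t(14), threshold 2.084.

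| Futility stop, % | SD 26 | SD 29 | SD 20 | SD 9 |
|---|---|---|---|---|
| Printed in 6.4 | 41.91 | 47.19 | 25.07 | 0.13 |
| −1.293, normal | 26.7 | 30.0 | 13.6 | 0.04 |
| −1.293, t(14) | 23.1 | 26.3 | 10.8 | 0.02 |
| −1.726, normal | 40.7 | 44.5 | 23.9 | 0.16 |
| −1.726, t(14) | 36.0 | 39.9 | 19.7 | 0.07 |
| −1.904, normal | 47.0 | 50.9 | 29.1 | 0.26 |
| −1.904, t(14) | 41.9 | 45.9 | 24.3 | 0.13 |

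Neither model fits one-sided 0.10 (−1.293). Under t(14) the table lies close to −1.904.

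**6. Power.** In a normal-model simulation with futility obeyed, power at SD 9 is 99.74 / 99.85 / 99.96% for c2 = −1.904 / −1.726 / −1.293. At SD 20 to 29, −1.904 costs about 5 to 6 points against −1.726. These figures depend on the model.

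**The case against.** **The slip is harmless.** It is conservative, the primary objective is safety and tolerability, futility is advisory, and at SD 9 almost every simulated trial stops early for efficacy. All of this stands. A reader might infer an inflated false-positive rate from a wrong critical value, but 3.98% is below both candidate levels.

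**The alpha conflict is narrower than it looks.** This also stands in part. A reader might count every mention of 10% as contradicting 4.3, but four of them are unsided and could be two-sided. The explicit contradiction is 4.2.1 against 4.3.

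**The CP formula is only a sign error.** This stands. Taken literally, the printed form gives CP of 77% at p = 0.08 and over 99.9% at p = 0.50, and a reader might conclude that futility can never be declared. The documents do not support that. SAP 4.3 defines CP in words as the chance of a significant reduction, the final rule rejects in the lower tail, and 6.4 prints futility rates of 25 to 47% at SD 20 to 29. The lower tail was intended.

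**The 6.4 table might reveal the cut-off used.** Only loosely. The t(14) match suggests that −1.904 was used in the simulation. However, if the same t statistic is judged for efficacy against the normal value 1.911 instead of 2.084, −1.726 gives 42.2 / 46.1 / 24.6 / 0.14%, about as close. On that variant −1.293 still misses, at 28.3 / 31.8 / 14.2%.

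**Conclusion.** The concern holds. On SAP 4.3's own inputs c2 is −1.726, not −1.904; this needs only the stated alphas, t = 0.80 and the usual joint normality of the two statistics. The conflicts between one-sided 0.05 (4.3) and one-sided 0.10 (4.2.1), and between 0.01 (4.2.5) and 0.028 (4.3, 6.4), are explicit, and nothing in the documents resolves them. They carry more weight than the arithmetic slip, because together they decide whether an interim p of 0.02 permits a stop and whether an interim p of 0.08 meets the futility trigger.

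The 6.4 table does not fit a one-sided alpha of 0.10. It was probably simulated with the printed −1.904, but that inference depends on the assumed t(14) model. The effect on power is under 1 point at the planning SD of 9. Larger losses at SD 20 to 29 are model-dependent, and any comparison with −1.293 applies only if one-sided 0.10 was intended.

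**What to change.** Before the unblinded interim:

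- State one overall alpha with its side and one interim efficacy threshold, identical in SAP 4.1, 4.2.1, 4.2.5, 4.3 and 6.4.
- Replace c2 with the matching value at t = 0.80. With interim 0.028, use −1.726 (one-sided 0.05) or −1.293 (one-sided 0.10). With interim 0.01, use −1.652 or −1.282.
- State that c2 is recomputed at the actual information fraction. SAP 4.3 lets N_CP and the stage proportions move but does not mention c2.
- Print CP = Φ{(c2 − B(t)/t)/√(1−t)}.
- Rerun the 6.4 table with that c2 and formula, and state the model behind its power figures.

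The cost is one constant, one formula, consistent wording in five sections and one simulation run. Choosing one-sided 0.05 tightens the level in 4.2.1. Choosing one-sided 0.10 means that the present 6.4 figures cannot be kept.

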4.4. Subject Disposition

A tabulation of subject disposition will be created, including the number screened, the number dosed with placebo, the number dosed with SYNBI020, the number in each subject population for analysis, the number that withdrew prior to completing the study, and reasons for withdrawal.

A by-subject listing of study completion information, including the reason for premature study withdrawal, if applicable, will be presented.

4.5. Demographic and Baseline Characteristics

Baseline, demographic and medical history information will be summarized for the SAF and SAF2 Populations using descriptive statistics. No formal statistical comparisons will be performed.

Demographic, baseline data and medical history will be provided in data listings.

Exposure to study drug will be shown in a by-subject listing for the SAF and SAF2 populations.

The demographic, baseline data and medical history data described above will be shown for Part 1 alone, Part 2 (by treatment), overall by treatment (Parts 1 and 2), and study overall (Parts 1 and 2 – all treatments) using descriptive statistics.

4.6. Safety Analyses

Safety analyses will be conducted using the SAF/SAF2 Populations.

4.6.1. Adverse Events

AEs will be coded using MedDRA and severity will be evaluated using the NCI CTCAE version 4.03. These will be displayed in tables and listings using System/Organ/Class (SOC) and Preferred Term (PT). AEs will also be presented by maximum severity.

AEs will be recorded from the time a subject signs informed consent through the safety follow-up period. Analyses will focus on any AE recorded, as well as treatment-emergent AEs (TEAEs), which are those events that have occurred after the start of the study drug.

AEs are summarized by subject incidence rates, therefore, in some tabulations, a subject contributes only once to the count for a given AE (SOC or PT). Several tabulations also show the total number of events, where a subject can contribute more than once.

The number and percentage of subjects, along with total number of events, with any AE, any TEAE, any TEAE assessed by the Investigator as related to treatment (definite, probable, or possible relationship), any AE resulting in discontinuation of study dosing and with any SAE will be summarized by treatment group and overall. In these tabulations, each subject will contribute only once (i.e., the most related occurrence or the most intense occurrence) to each of the incidence rates in the descriptive analysis, regardless of the number of episodes.

Tabulations will also be presented by MedDRA SOC and PT for the following: all TEAEs, related TEAEs, TEAEs by severity and TEAEs leading to permanent study drug withdrawal.

No formal hypothesis-testing analysis of AE incidence rates will be performed.

All AEs occurring on study will be listed in subject data listings.

By-subject listings also will be provided for the following: subject deaths; SAEs; AEs leading to withdrawal and Grade 3 or 4 AEs, and narratives will be shown for these.

4.6.2. Laboratory Data

Clinical laboratory values will be expressed using SI units and will be measured during screening, on Day -2 (Baseline), Day 4, Day 6 and Day 7.

The following will be performed:

- Alkaline phosphatase, total bilirubin, direct bilirubin, CO₂, chloride, glucose, potassium, AST, ALT, sodium, albumin, total protein, phosphorous, calcium, activated partial thromboplastin time (aPTT), international normalized ratio (INR), prothrombin time (PT), CBC with differential, C-reactive protein, follicle-stimulating hormone (FSH, for women), blood urea nitrogen (BUN) and creatinine
- Urinalysis

The actual value and change from Baseline to each on study evaluation will be summarized for each clinical laboratory parameter. In the event of repeat values, the last non-missing value per study day/time will be used. Hematology, chemistry and urinalysis will also be displayed by the number and percent of subjects with normal, abnormal and clinically significant abnormal in shift from baseline tables at each visit.

All laboratory data will also be provided in data listings. Clinical significance and abnormality will be indicated within these listings.

4.6.3. Vital Signs and Physical Examinations

Semi-supine vital signs will be collected during screening, every 8 hours during the dosing period (Day -5 – Day 6), Day 7 and Day 14.

The following will be collected: systolic blood pressure (BP), diastolic BP, pulse and body temperature. Subjects are required to remain in the semi-supine position for at least 5 minutes prior to obtaining vital signs.

The actual value and time-matched change from Baseline (or Screening) to each on study evaluation will be summarized for vital signs. Vitals will also be displayed by the number and percent of subjects with normal, abnormal and clinically significant abnormal.

By-subject listings of vital sign measurements will be presented in data listings.

Physical examinations will be performed during screening and Day -5; and symptom-driven on Day 7 and Day 14.

Any abnormal physical examination findings will be recorded as AEs and included in AE outputs.

4.6.4. Electrocardiogram

A semi-supine single 12-lead ECG will be performed during screening, Day -2 (Baseline), Day 4 and Day 7.

The following will be collected: RR, QT, QRS and PR intervals. Fridericia's formula should be used to calculate the QT interval corrected for heart rate (QTcF).

The actual value and change from Baseline (or Screening) to each on study evaluation will be summarized for ECGs.

ECG results will also be summarized descriptively, including the number and percent of subjects with normal, abnormal and clinically significant abnormal results at Baseline and each study visit.

All ECG data for each subject will be provided in data listings.

4.6.5. FibroScan

A FibroScan (vibration-controlled transient elastography) will be performed once at Day -2 (Baseline) to quantify liver fibrosis.

FibroScan results for each subject will be provided in data listings.

4.6.6. Blood and Urine Cultures/Polymerase Chain Reaction

Blood and urine cultures and/or PCR will be performed as needed according to standard clinical practice if clinical presentation warrants. This may include, but is not limited to, cases in which subjects develop persistent (> 24 hours) fever, chills, night sweats, or other symptoms suggestive of local or systemic clinical infection.

4.6.7. Hepatic Encephalopathy Severity Grading

HE severity grading will be collected via the West Haven Grading System on Day -2 (Baseline) and Day 6.

HE grades will be summarized descriptively, including the number and percent of subjects at each grade on Day -2 (Baseline) and Day 6.

All HE data for each subject will be provided in data listings.

[REDACTED]

[REDACTED]

[REDACTED]

[REDACTED]

4.6.9. Cirrhosis Severity Grading

Severity of cirrhosis will be assessed by the Child-Turcotte-Pugh score, which reflects a composite score incorporating HE grade, extent of ascites, and bilirubin, albumin, and INR values and MELD score calculated based on bilirubin, creatinine, and INR values. This will be collected during screening, Day -2 (Baseline) and Day 6.

Cirrhosis severity results will be summarized descriptively for each class at every time point it was collected. The composite Child-Turcotte-Pugh and MELD scores will also be summarized by their actual score and change from Baseline to each on study evaluation.

All cirrhosis severity data for each subject will be provided in data listings.

4.6.10. Concomitant Medications

Concomitant medications will be coded using the WHO Drug Dictionary. Results will be tabulated by Anatomic Therapeutic Class (ATC) and preferred term.

The use of concomitant medications will be included in by-subject data listing.

4.7. Pharmacodynamic Evaluations

PD analyses will be conducted using the PD Population. Urine and blood samples will be collected at screening and on study both before and after administration of SYNBI020 or placebo for PD measurements.

All PD parameters of SYNBI020 will be summarized in tables, listings, and figures (Section 6); no formal statistical analysis will be performed, with the exception of venous ammonia AUC and fasting spot venous ammonia. Additional post-hoc exploratory PD analyses of interest may be carried out, in addition to those described below.

4.7.1. Venous Ammonia Area under the Curve

Samples for venous ammonia will be drawn relative to meal times. In order to analyze AUC₀₋₂₄, subjects must complete all 3 ammonia AUC intervals (Baseline, Day 5 and Day 6).

To calculate the AUC over 24 hours (AUC₀₋₂₄), the linear trapezoidal method will be utilized, with the following formula:

$$AUC_{0-24} = \sum \frac{(t_i - t_{i-1})(A_i + A_{i-1})}{2}$$

Symbol	Definition
\sum	Summation over all times, i
t_i	Time point, in hours
t_{i-1}	Previous time point, in hours
A_i	Venous ammonia measurement at time i
A_{i-1}	Venous ammonia measurement at previous time point, $i-1$

Once AUC₀₋₂₄ is calculated, this will be divided by 24 to obtain the average daily ammonia.

Statistical analysis will be performed on log-transformed venous ammonia AUC₀₋₂₄ as a mixed-model with repeated measures with baseline as a covariate, a fixed effect by treatment (Day 5 and 6 treated as repeated measures on treatment, not differentiated by day), and a random effect by subject. Results will be transformed back to the linear scale for reporting; at the Sponsor's option, results may be normalized to the average (or weighted-average based on number of subjects) upper limit of normal across the labs used in the study.

A bar chart will be generated illustrating the mean change from baseline (average of Day 5 and Day 6 minus baseline) in AUC₀₋₂₄ for ammonia on the y-axis, bar fill color will indicate active (black) or placebo (white), and subjects across all treatment groups will be sorted in order from

greatest mean change from baseline (left) to least mean change from baseline (right). The bar chart will be generated twice, once for the PD population in Part 2 and once for the PD population in the full study (Part 1 and Part 2). (For clarity, this representation is sometimes referred to as a “waterfall plot”.)

4.7.2. Fasting Spot Venous Ammonia

In addition to tables, listings, and figures for descriptive statistics (Section 6), statistical analysis will be performed on log-transformed fasting spot venous ammonia (defined as the ammonia measurement during the day) to assess change from baseline and change from placebo. The statistical model for fasting spot venous ammonia will be a mixed-model with repeated measures with baseline as a covariate, fixed effects by day and treatment, and a random effect by subject. Results will be transformed back to the linear scale for reporting; at the Sponsor’s option, results may be normalized to the average (or weighted-average based on number of subjects) upper limit of normal across the labs used in the study.

4.8. Microbiotic-Kinetic Evaluations

MK analyses will be conducted using the MK Population. Additional post-hoc exploratory MK analyses of interest may be carried out, aside from what is described below.

MK variables will be calculated from the serial fecal sampling from each subject. One baseline fecal sample is required to be collected prior to SYNBI020 dosing (i.e., any time from Day -5 through Day 1) and daily following dosing through Day 7. Feces will continue to be collected weekly for the first 6 weeks following discharge and every other week until a subject has a negative SYNBI020 fecal test for up to 10 weeks following completion of study dosing.

The variables to be determined and the time points of determination are summarized below:

Table 2 Microbiotic-Kinetic Parameters for Analysis

Parameter	Description
T _{lag}	The time of the first detectable fecal SYNBI020
T _{ss}	The time to steady-state
q _{max}	The maximum observed fecal SYNBI020 qPCR signal
T _{last}	The time of the last detectable fecal SYNBI020
Half-life	The time for the fecal SYNBI020 PCR signal to decline by 50%

A sample will be considered negative for the purposes of SYNBI020 clearance if it is BQL, and therefore SYNBI020 clearance is the same as T_{last}.

Missing values will not be imputed, and if sufficient data are missing for a given subject, that subject may be considered non-evaluable for MK analysis and would not be included in the MK Population.

All MK parameters of SYNBI020 will be summarized in tables and in listings; no formal statistical analysis will be performed.

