7.5.2. Follow-up After Completion of Study Dosing

One week (7 ± 1 days) after discharge from the inpatient unit, subjects will return for clinical evaluation and bring a 1-week post-dose fecal sample. Subjects will be provided diary cards for collection of AE data. Feces will continue to be collected weekly for the first 6 weeks following discharge and biweekly until a subject has a negative SYNB1020 fecal test for up to 10 weeks following completion of study dosing. Subjects who remain colonized with SYNB1020 after 10 weeks following the last dose will be treated with a 3-day course of oral ciprofloxacin. Subjects who are allergic to ciprofloxacin can be treated with antibiotics based on reported sensitivity at the investigator's discretion. Refer to the SYNB1020 Investigator's Brochure for further details. A SYNB1020 fecal test will be performed 3 to 5 days following completion of antibiotic treatment solely for research purposes and will not guide subject follow-up decision making. An AE assessment will be performed by telephone at least 7 days after completion of antibiotic treatment. If no AEs are reported, subjects will not require any further follow-up and will be considered to have completed the study requirements. If AEs are reported, subjects will be advised to return to the inpatient facility for a comprehensive physical examination, laboratory assessment, and AE causality determination.

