4.2.9. Visit Windows

Screening procedures must be performed to determine eligibility for enrollment in both Part 1 and Part 2 within 30 days prior to admission to the inpatient facility.

During inpatient monitoring, visit windows are not a concern.

The protocol-specified visit window for the End of Study (EOS)/Discharge Visit to occur is at least 12 hours after completion of the last dose (Day 7); subjects who withdraw early should have this visit within 24 hours of discontinuation of the study drug. The first follow-up visit is specified in the protocol as occurring 7 ± 1 day after the EOS Visit, and subjects will be followed for up to 10 weeks after this first follow-up visit occurs. For continuation of follow-up visits, subjects will be required to provide weekly fecal samples (7 ± 1 day after the follow-up visit) for the first 6 weeks following discharge, and bi-weekly (14 ± 1 day) until the subject has

a negative SYNBI020 fecal test (up to 10 weeks after completion of study). However, all data will be analyzed regardless of visit windows.

Table 1 Visit Windows

Evaluation	Protocol-Specified Interval
Screening	Day -36 to Day -6
Part 1 Inpatient	Day -5 to Day 7
Part 2 Inpatient	Day -5 to Day 7
EOS/Discharge	Day 7 (12 hours post-dose)
Follow-Up	Day 13 to Day 15

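### SAP 4.8 equates SYNB1020 clearance with T_last, which is wrong for a subject who completes the study still positive at the 10-week limit

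*SAP*

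**What the plan says.** **Definition.** SAP 4.8 defines T_last as the time of the last detectable fecal SYNB1020. A stool is negative for clearance "if it is BQL, and therefore SYNBI020 clearance is the same as" T_last. SAP Section 5 declares the BQL-only rule as a clarification of the protocol.

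**Source data.** "MK variables will be calculated from the serial fecal sampling from each subject" (SAP 4.8). The parameters are summarized descriptively, with no formal analysis.

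**Collection.** Stools are weekly for six weeks after discharge, then "biweekly until a subject has a negative SYNB1020 fecal test for up to 10 weeks following completion of study dosing" (Protocol 7.5.2).

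**Positive at the limit.** "Subjects who remain colonized with SYNB1020 after 10 weeks following the last dose will be treated with a 3-day course of oral ciprofloxacin" (Protocol 7.5.2). Then: "A SYNB1020 fecal test will be performed 3 to 5 days following completion of antibiotic treatment solely for research purposes". If the closing telephone call brings no adverse event, these subjects "will be considered to have completed the study requirements".

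**Nearest handling rules.** SAP 4.8 does not impute, and "if sufficient data are missing for a given subject, that subject may be considered non-evaluable for MK analysis". SAP 4.2.1.1 gives values to BQL results before, between and after quantifiable ones. SAP 3.1 limits the MK population to safety-population subjects who completed the study and were judged evaluable for MK data.

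**The concern.** A rule for calling a single stool negative does not turn the last positive stool into a clearance time. That step also needs a later negative stool, and SAP 4.8 does not require one. Without it, all that is known is that clearance came after T_last, if at all.

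Fecal kinetics is a secondary objective, and the outpatient follow-up exists to track clearance. The subject affected would be the slowest to clear. If T_last is read as clearance, the longest clearance time in the report would be understated, and a subject whom the protocol regards as colonized, and treats for it, would appear as cleared.

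**Working it through.** The plan states no figure to reproduce. The check applies the definitions to the stool schedule and then looks for a rule that would catch the case.

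**1. Schedule.** Last dose is Day 6 and discharge is Day 7 (Protocol 4.2.3).
- Weekly stools: 7 + 7k for k = 1 to 6, giving Days 14, 21, 28, 35, 42 and 49.
- Biweekly stools: 49 + 14 = Day 63; 63 + 14 = Day 77.
- Ten weeks after the last dose: 6 + 70 = Day 76. Day 77 lies within the one-day window of SAP 4.2.9.
- SAP 4.2.9 also counts ten weeks from the first follow-up visit: 14 + 70 = Day 84. The next biweekly stool would be 77 + 14 = Day 91, so Day 77 remains the last scheduled stool.

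**2. A BQL stool follows the last positive.** Clearance lies between the two stools. With no missed sample, T_last precedes the first BQL stool by at most one sampling interval: 7 days in the weekly phase, 14 in the biweekly phase. The error is bounded.

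**3. Quantifiable at the 10-week stool.** T_last is about Day 76 or 77, which is 70 or 71 days after the last dose (76 − 6 = 70; 77 − 6 = 71). SAP 4.8 makes that the clearance time. The data show only that clearance exceeds it, and the schedule sets no upper limit on the shortfall.

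**4. Does another rule catch case 3?**

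| Rule | Result for this subject |
|---|---|
| SAP 3.1, completion | Met under Protocol 7.5.2 if no adverse event is reported at the closing call |
| SAP 4.8, missing data | Nothing is missing |
| SAP 4.2.1.1, BQL values | The last value is quantifiable, so the rule is silent |
| Protocol 10.3, calculation only where the data allow | T_last can be calculated; only the label clearance is unsupported |

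**5. Post-antibiotic stool.** Assume the 3-day course starts on Day 77. It ends on Day 79, and the test falls on Days 82 to 84 (79 + 3 to 79 + 5). SAP 4.8 does not say whether this stool counts. A BQL result follows ciprofloxacin and does not show that the subject cleared unaided. A quantifiable result would move T_last past the antibiotic.

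**6. Effect on the summary.** SAP 4.2.1 summarizes discrete numeric variables, with T_lag as its example, by median, minimum and maximum. Assume T_last is handled likewise and that the active arm has 10 MK subjects (20 planned in SAP 4.3, randomized 1:1).
- A subject whose first BQL stool is at Day 77 has T_last no later than Day 63, so any case 3 value ranks at the top.
- One such subject sets the maximum.
- The median is the mean of the 5th and 6th ordered values. It contains no case 3 value until at least 5 of the 10 subjects are still positive.

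**The case against.** **The harm is not certain.** The parameter table in SAP 4.8 has no row for clearance time. It has T_last, which is correctly stated for a subject positive at 10 weeks. The list of statistical tables (SAP 6.1) is not in the supplied text, so whether any output labels T_last as clearance cannot be checked. This stands as a limit on the consequence. It does not repair the sentence in SAP 4.8, which states the equivalence outright.

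**Discretion exists.** Protocol 10.3 calculates the variables only where the data allow, and SAP 3.1 requires a judgment of evaluability that is not confined to missing samples. Either could be used to withhold a value. Neither says to do so here, and withholding would drop the most informative subject when a censored value could be reported.

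**It may not happen.** In the healthy-volunteer study (Protocol 2.2.2.1), all 44 subjects who had completed cleared within about four weeks and none needed antibiotics. Eight were still in follow-up, and patients with cirrhosis may differ. Rarity is a fair point on size.

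**It is visible and does not affect care.** Listing 16.4.1.2 shows the fecal qPCR results, and antibiotic decisions follow the stool test, not T_last. Both points stand.

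**Stronger readings a reader might infer.**
- That every subject whose last stool is quantifiable is affected. Subjects who withdraw or are lost while positive are not study completers, so SAP 3.1 already keeps them out of the MK population.
- That collection could stop early on a quantifiable stool, because Protocol 10.3 also counts as negative a stool estimated below 0.1% of the dose. Protocol 7.5.2 does not refer to that criterion. SAP Section 5 replaces it with BQL only and cites a note to file that is not supplied. The documents do not establish this route.

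**Conclusion.** The equation of clearance with T_last is wrong for one defined case: a subject who completes the study while still quantifiable at the 10-week limit. The protocol plans for that case, and neither document says how to report it.

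The point is minor. It concerns one descriptive secondary parameter, chiefly its maximum. The number of subjects affected cannot be estimated from the documents and may be zero. The safety endpoints and ammonia analyses are unaffected. A general claim that reported clearance times will be too short is not supported: when a BQL stool follows, the gap is at most one sampling interval.

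The conclusion assumes that the treated subject is judged evaluable for MK data and that no unsupplied document already sets a censoring rule. The effect on the maximum further assumes that T_last is summarized in the same way as T_lag.

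**What to change.** In SAP 4.8, replace the statement that clearance is the same as T_last with two sentences to this effect:

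- Clearance is shown only when a BQL stool, collected before any antibiotic course, follows the last quantifiable stool.
- Otherwise the subject is reported as not shown to be cleared, with the time right-censored at the last pre-antibiotic stool (written as > T_last) and any post-antibiotic result listed separately.

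T_last can stay in the parameter table under its own name. The pre-antibiotic condition is a recommendation, since the documents do not define clearance as unaided. It fits Protocol 7.5.2, which gives the later stool a research purpose only.

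The cost is two sentences before database lock. The change needs no protocol amendment, extra stools or antibiotic courses, and it avoids deciding after the fact how to label a persistently colonized subject.
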